Overall Rationale for the Amendment: The primary objectives of this amendment are to change the dose-escalation design in each treatment group from an accelerated titration to a conventional 3 + 3 approach, to refine the eligibility criteria to only include subjects with advanced hematological malignancies unresponsive to currently available therapy and for whom there is no standard of care available, and to update the dose-limiting toxicity criteria as appropriate to the diseases included in each dose-escalation treatment group.

1. Synopsis; Section 4, Investigational Plan; Section 9.2, Selection of Sample Size

Description of change: The dose-escalation design in each treatment group was updated from an accelerated titration followed by a modified Toxicity Probability Interval design to a standard 3 + 3 design. Additionally, the estimated sample size was updated accordingly.

Rationale: Change requested by FDA.

2. Synopsis; Section 3, Subject Eligibility

Description of change: The eligibility criteria and description of the study population were updated to only include subjects with advanced hematological malignancies unresponsive to currently available therapy and for whom there is no standard-of-care therapy available.

Rationale: Change requested by FDA.

3. Section 5.2.3, Dose-Limiting Toxicity and Determination of Maximum Tolerated Dose

Description of change: Dose-limiting toxicity criteria in Part 1 were modified, consistent with FDA requests, for Treatment Group A, Treatment Group B, and Treatment Group C (added in current amendment) and were applied as appropriate to the diseases included in each group.

Rationale: Change requested by FDA.

4. Synopsis; Section 3, Subject Eligibility; Section 4, Investigational Plan; Section 5.2, Treatment of Subjects; Section 7.8.4, Food-Effect Pharmacokinetic Testing

Description of change: Treatment Group A and Expansion Cohort A were updated to include only subjects with leukemia and MDS; MDS/MPN (including atypical chronic myeloid leukemia [aCML], chronic myelomonocytic leukemia [CMML], myelodysplastic/ myeloproliferative neoplasm unclassifiable [MDS/MPN-U], and refractory anemia with ring sideroblasts and thrombocytosis [RARS-T]) and MF were removed from these groups. Treatment Group C and Expansion Cohort D, which include only subjects with MDS/MPN and MF, were added to Part 1 and Part 2, respectively. Accordingly, appropriate detail was added to all of the relevant Protocol sections, including study design and investigational plan, subject eligibility and number of subjects, dose-limiting toxicity and dose interruption/ adjustment criteria, and pharmacokinetic assessments, consistent with the newly defined treatment group.

CONFIDENTIAL

CONFIDENTIAL

Rationale for change: Per FDA request, Treatment Group B dose-limiting toxicity criteria were applied to subjects with MDS/MPN and MF. To optimally assess the safety and tolerability of INCB053914 in subjects with these diseases, separate dose-escalation and expansion groups that include only MDS/MPN and MF were added to the study Protocol.

5. **Synopsis; Section 2.2.2, Secondary Endpoints**

Description of change: Secondary endpoint pertaining to pharmacokinetic assessment time point at Day 15 was changed to Day 8.

Rationale for change: Endpoint was updated to reflect correct visit day at which steady-state and serial PK sampling is performed.

6. **Incorporation of administrative changes.** Other minor, administrative changes have been incorporated throughout the Protocol and are noted in the red-line/strike-out version of the amendment.

CONFIDENTIAL

CONFIDENTIAL

Figure 2:	Combination Therapy Study Design	18

LIST OF ABBREVIATIONS

Abbreviation	Term
aCML	atypical chronic myeloid leukemia
AE	adverse event
ALP	alkaline phosphatase
ALT	alanine aminotransferase
AML	acute myeloid leukemia
AST	aspartate aminotransferase
AUC _{0-t}	AUC from time zero (predose) to time of last observed quantifiable concentration within a subject across all treatments
BID	twice daily
BOR	best overall response
bpm	beats per minute
BSA	body surface area
CCyR	complete cytogenetic response
CI	confidence interval
Cl/F	oral dose clearance
CLL	chronic lymphocytic leukemia
C _{max}	maximum observed concentration
C _{min}	minimum observed concentration
CMML	chronic myelomonocytic leukemia
CMR	complete molecular response
CR	complete remission/response
CRF	case report form
CRi	complete remission with incomplete hematologic recovery
CRp	complete remission with incomplete platelet recovery
CT	computed tomography
CTCAE	Common Terminology Criteria for Adverse Events
CTEP	Cancer Therapy Evaluation Program
C-TG	combination treatment group
DLBCL	diffuse large B-cell lymphoma
DLT	dose-limiting toxicity

CONFIDENTIAL

CONFIDENTIAL

Abbreviation	Term
█	█
ECG	electrocardiogram
ECOG	Eastern Cooperative Oncology Group
eCRF	electronic case report form
█	█
ELN	European LeukemiaNet
EOT	end of treatment
█	█
FAS	full analysis set
FDA	Food and Drug Administration
FISH	fluorescence in situ hybridization
HI	hematologic improvement
HI-E	hematologic improvement – erythroid response
HI-N	hematologic improvement – neutrophil response
HI-P	hematologic improvement – platelet response
I-DAC	intermediate-dose cytarabine
IV	intravenously
IWCLL	International Workshop on Chronic Lymphocytic Leukemia
IWG	International Working Group
IWG-MRT	International Working Group-Myeloproliferative Neoplasms Research and Treatment
KM	Kaplan-Meier
LCM	left costal margin
L-DAC	low-dose cytarabine
MDS	myelodysplastic syndrome
MedDRA	Medical Dictionary for Regulatory Activities
MF	myelofibrosis
MLFS	morphologic leukemia-free state
MM	multiple myeloma
MPN	myeloproliferative neoplasms
█	█
MPN-U	myeloproliferative neoplasms unclassifiable

CONFIDENTIAL

CONFIDENTIAL

Abbreviation	Term
MR	minimal response
MRI	magnetic resonance imaging
MTD	maximum tolerated dose
NA	not assessed
NCI	National Cancer Institute
NE	nonevaluable
NONMEM	nonlinear mixed-effect modeling
ORR	objective remission/response rate
█	██████████
PAD	pharmacologically active dose
pBAD	phosphorylated Bcl-2-associated death promoter protein
PCyR	partial cytogenetic response
PD	pharmacodynamics
PET	probability of early termination
PET-MF	post-essential thrombocythemia myelofibrosis
█	██████████
█	████████████████████
PIM	proviral integration site of Moloney murine leukemia virus
PK	pharmacokinetic
PMF	primary myelofibrosis
PMR	partial molecular response
PP	per protocol
PPV-MF	post-polycythemia vera myelofibrosis
PR	partial remission/response
PT	preferred term
QD	once daily
QRS	Combination of three of the graphical deflections on an ECG. It is usually the central and most visually obvious part of the tracing. It corresponds to the depolarization of the right and left ventricles of the human heart.
QTcF	QT interval corrected using the Fridericia formula
RARS-T	refractory anemia with ring sideroblasts and thrombocytosis
RD	relapse disease
RNA	ribonucleic acid

Abbreviation	Term
RP2D	recommended Phase 2 dose
RR	ECG interval from the beginning of a QRS complex to the beginning of the next QRS complex
SAE	serious adverse event
SAP	statistical analysis plan
SC	subcutaneously
sCR	stringent complete response
SD	stable disease
SI units	International System of Units
SOC	system organ class
TEAE	treatment-emergent adverse event
TGA	Treatment Group A
TGB	Treatment Group B
TGC	Treatment Group C
T _{max}	time of occurrence of C _{max}
UE	unable to evaluable
VGPR	very good partial response
WBC	white blood cell
WHO	World Health Organization

1. INTRODUCTION

This is an open-label, dose-escalation study of the pan-PIM kinase inhibitor INCB053914 as monotherapy and in combination with standard-of-care agents in subjects with advanced malignancies. The study will be conducted in 4 parts: Parts 1 and 2 will evaluate INCB053914 as monotherapy, and Parts 3 and 4 will evaluate INCB053914 in combination with cytarabine, azacitidine, or ruxolitinib. Section 1 of the Protocol provides a detailed description of the investigational product, target patient population, rationale for doses to be examined, and potential risks and benefits of treatment with INCB053914 and selected standard-of-care agents.

The purpose of this SAP is to provide details of the statistical analyses that have been outlined in the Study INCB 53914-101 Protocol. The scope of this plan includes the interim and final analyses that are planned and will be executed by the Department of Biostatistics or designee, and the analyses of PK.

2. STUDY INFORMATION, OBJECTIVES, AND ENDPOINTS

2.1. Protocol and Case Report Form Version

This SAP is based on INCB 53914-101 Protocol Amendment 6 dated 15 MAR 2017 and CRFs approved 27 JUN 2017. Unless superseded by an amendment, this SAP will be effective for all subsequent Protocol amendments and CRF versions.

2.2. Study Objectives

2.2.1. Primary Objectives

- All parts: To evaluate the safety and tolerability of INCB053914 as a monotherapy and in combination with standard-of-care agents in subjects with advanced malignancies.
- Part 4 only:
 - To evaluate the efficacy of INCB053914 in combination with cytarabine in subjects with relapsed or refractory AML based on ORR.
 - To evaluate the efficacy of INCB053914 in combination with azacitidine in subjects with newly diagnosed AML who are 65 years or older and unfit for intensive chemotherapy based on ORR.

2.2.2. Secondary Objectives

- All parts: To evaluate the PK of INCB053914 when administered alone in the fasted state, the effect of food on the INCB053914 PK, and the PK when administered in combination with SOC agents in the fasted state.
- All parts: To assess the PD of INCB053914 as a monotherapy and in combination with standard-of-care agents in subjects with advanced malignancies.

- [REDACTED]
- | [REDACTED]
- [REDACTED]
- | [REDACTED]
- | [REDACTED]
- | [REDACTED]
- [REDACTED]
- | [REDACTED]
- | [REDACTED]
- | [REDACTED]

2.3. Study Endpoints

2.3.1. Primary Endpoints

- Safety and tolerability will be assessed by monitoring frequency, duration, and severity of AEs and DLTs; through physical examinations; by evaluating changes in vital signs and ECGs; and through clinical laboratory blood and urine sample evaluations.
- Part 4 only: ORR, defined as the proportion of subjects who achieve CR or CRi.

2.3.2. Secondary Endpoints

- PK of INCB053914, including C_{max} , T_{max} , C_{min} , AUC_{0-t} , Cl/F at timepoints specified in the Protocol, Section 6.
- PD profile of INCB053914 defined by pBAD.
- [REDACTED]
- [REDACTED]

[REDACTED]

3. STUDY DESIGN

[figure not shown]
This is an open-label, dose-escalation study of the PIM kinase inhibitor INCB053914 as monotherapy and in combination with standard-of-care agents in subjects with advanced malignancies. Subjects will receive INCB053914 in 21- or 28-day cycles (as applicable to regimen schedules) until withdrawal criteria are met. Alternative administration schedules may be assessed if indicated by emerging safety, PK, or PD data. The study will be conducted in 4 parts: Parts 1 and 2 will evaluate INCB053914 as monotherapy (Figure 1) and Parts 3 and 4 will evaluate INCB053914 in combination with select standard-of-care agents (Figure 2).

Part 1 (monotherapy dose escalation) will be conducted in 2 disease-specific treatment groups (TGA and TGB, respectively) and will determine the MTD of INCB053914 and/or a tolerated PAD (defined as a plasma concentration exceeding average PK that is projected to inhibit pBAD level > 50% for approximately 12 hours) that will be taken forward into Part 2 of the study (ie, the RP2D). Treatment Group A will include acute leukemia, high-risk MDS, and MDS/MPNs (including aCML, CMML, MDS/MPN-U, and RARS-T). Treatment Group B will include MM, lymphoma, and other lymphoproliferative neoplasms. Dose escalation for TGA and TGB will proceed independently, with each treatment group following a 3 + 3 design. At least 3 subjects will be enrolled and treated in each cohort. If no DLTs are observed in the initial 3 subjects, the next cohort will begin enrollment at the next higher dose level. If 1 DLT is observed in the first 3 subjects, 3 additional subjects will be enrolled in that cohort. If a DLT occurs in one-third or more of the total cohort (ie, ≥ 2 of 6 subjects), then the MTD will be deemed to have been exceeded, and the next lower dose level will be deemed to be the MTD. Thus, the MTD will be defined as 1 dose level below that at which one-third or more of subjects in a particular cohort report DLTs. If the first cohort exceeds the MTD, a dose de-escalation will be considered.

Part 2 (monotherapy dose expansion) will further evaluate the safety, efficacy, PK, and PD of the RP2D in specific disease indications in which PIM kinases are particularly relevant, including leukemias and myeloproliferative and lymphoproliferative disorders, such as AML, MDS/MPN, MF, MM, and DLBCL. The 5 expansion cohorts are as follows:

- **TGA Expansion Cohort 1 (TGA A1):** At least 5 and up to approximately 15 subjects with AML will be enrolled and treated at the RP2D identified in Part 1 TGA.
- **TGA Expansion Cohort 2 (TGA A2):** At least 5 and up to approximately 15 subjects with MDS/MPN (including aCML, CMML, MDS/MPN-U, and RARS-T) will be enrolled and treated at the RP2D identified in Part 1 TGA.
- **TGA Expansion Cohort 3 (TGA A3):** At least 5 and up to approximately 15 subjects with MF will be enrolled and treated at the RP2D identified in Part 1 TGA.
- **TGB Expansion Cohort 1 (TGB B1):** At least 5 and up to approximately 15 subjects with MM will be enrolled and treated at the RP2D identified in Part 1 TGB.
- **TGB Expansion Cohort 2 (TGB B2):** At least 5 and up to approximately 15 subjects with DLBCL will be enrolled and treated at the RP2D identified in Part 1 TGB.

Figure 1: Monotherapy Study Design

Part 3 (combination dose-finding) will consist of up to 3 disease-specific combination treatment groups (C-TGA, C-TGB, and C-TGC) and will determine the MTD and/or a tolerated PAD of INCB053914 in combination with the selected standard-of-care agents. The combination dose-finding will use a 3 + 3 design to identify an optimal dose regimen in up to 3 different combination expansion cohorts. The possible combination expansion cohorts are as follows:

- **Combination Treatment Group A (C-TGA):** INCB053914 + cytarabine in subjects with relapsed/refractory AML.
- **Combination Treatment Group B (C-TGB):** INCB053914 + azacitidine in subjects with relapsed/refractory AML or elderly subjects (≥ 65 years) with newly diagnosed AML (*de novo* or secondary) who are unfit to receive intensive chemotherapy.
- **Combination Treatment Group C (C-TGC):** INCB053914 + ruxolitinib in subjects with primary or secondary MF (PPV-MF or PET-MF) who have had an inadequate response to ruxolitinib monotherapy, defined as follows:
 - Palpable spleen of > 10 cm below the left subcostal margin on physical examination at the screening visit OR
 - Palpable splenomegaly of 5 to 10 cm below left subcostal margin on physical examination and active symptoms of MF at the screening visit as demonstrated by presence of 1 symptom score ≥ 5 or 2 symptom scores ≥ 3 using the Screening Symptom Form ([Appendix N](#)).

[figure not shown]
Between 3 and up to approximately 10 subjects will be enrolled into cohorts under each of the SOC treatment groups, C-TGA, C-TGB, and C-TGC, as described above. Dose-finding for C-TGA, C-TGB, and C-TGC will proceed independently, with each treatment group following a 3 + 3 cohort design. At least 3 subjects will be enrolled and treated at each dose level. If no DLTs are observed in the initial 3 subjects, the next cohort will begin enrollment at the next higher dose level of INCB053914. If 1 DLT is observed in the first 3 subjects, 3 additional subjects will be enrolled in that cohort. If a DLT occurs in one-third or more of the total cohort (ie, ≥ 2 of 6 subjects), then the MTD will be deemed to have been exceeded, and the next lower dose level will be deemed to be the MTD. Thus, the MTD will be defined as 1 INCB053914 dose level below that at which one-third or more of subjects in a particular cohort report DLTs. If the first cohort exceeds the MTD, a dose de-escalation of INCB053914 will be considered.

Part 4 (combination dose expansion) will further evaluate the safety, efficacy, PK, and PD of the selected combination dose regimens identified in Part 3 in up to 3 expansion cohorts in specific indications relevant to the drug combinations (2 AML; 1 MF). The 2 AML expansion cohorts will use a Simon 2-stage design to evaluate the efficacy of the combination regimens.

- **C-TGA Expansion Cohort 1 (C-TGA E1)** will enroll relapsed/refractory (r/r) AML subjects who will be treated with INCB053914 in combination with I-DAC using the regimen identified in Part 3. This cohort will use a Simon 2-stage design. If an insufficient number of responders is observed in the cohort at Stage 1, further enrollment in the cohort will be terminated.

- **C-TGB Expansion Cohort 1 (C-TGB E1)** will enroll subjects with newly diagnosed AML (*de novo* or secondary) who are ≥ 65 years at screening and unfit to receive intensive chemotherapy and who will be treated with INCB053914 in combination with azacitidine using the regimen identified in Part 3. This cohort will use a Simon 2-stage design. If an insufficient number of responders is observed in the cohort at Stage 1, further enrollment in the cohort will be terminated.
- **C-TGC Expansion Cohort 1 (C-TGC E1)** will enroll up to 16 subjects with PMF or secondary MF (PPV-MF or PET-MF) who have had an inadequate response to ruxolitinib monotherapy and who will be treated with INCB053914 in combination with ruxolitinib using the dose identified in Part 3.
- **Optional C-TGA Expansion Cohort 2 (C-TGA E2):** If the Part 3 C-TGB dose-finding does not yield a tolerable combination of INCB053914 and azacitidine, or if the Part 4 C-TGB E1 Simon Stage 1 does not yield favorable efficacy data, then the sponsor may elect to evaluate INCB053914 in combination with a L-DAC regimen in this population. This option will use an INCB053914 dose deemed tolerable in combination with I-DAC and will reference safety and tolerability data obtained from the Part 3 C-TGA dose-finding. If the sponsor and investigators believe that the optimal dose regimen of INCB053914 in combination with L-DAC will be different from that of INCB053914 in combination I-DAC, a separate dose-finding cohort will be initiated to identify the optimal dose regimen of INCB053914 in combination with L-DAC.

Figure 2: Combination Therapy Study Design

3.1. Control of Type I Error

For the primary efficacy endpoint in Part 4, the 1-sided Type I error will be controlled at 0.05 for each individual cohort expansion. Note that this level of significance does not account for the multiple expansion cohorts. For other endpoints, CIs will be reported at a 95% confidence level.

3.2. Sample Size Considerations

3.2.1. Sample Size in Part 1

In Part 1, a 3 + 3 dose escalation design will be used in 2 disease-specific treatment groups. Dose escalation for the 2 treatment groups will proceed independently. A minimum of 3 and up to 6 evaluable subjects will be enrolled at each dose level. The total sample size in Part 1 will depend on the frequency of DLTs and the number of dose levels tested before the MTD or PAD is reached.

3.2.2. Sample Size in Part 2

In Part 2, up to 5 expansion cohorts will consist of at least 5 and up to approximately 15 subjects each treated at the RP2D identified in the corresponding Part 1 treatment group. With 5 subjects

enrolled, there is an 83% probability of observing at least 1 responder if the true underlying response rate is 30%.

3.2.3. Sample Size in Part 3

In Part 3, a 3 + 3 design will be used in up to 3 disease-specific treatment groups to identify an optimal dose regimen. Dose escalation for 3 treatment groups will proceed independently. A minimum of 3 and up to 6 subjects will be enrolled in each dose cohort. The total number of subjects will depend on the frequency of DLTs and the number of dose levels tested before the MTD or PAD is reached.

3.2.4. Sample Size in Part 4

In Part 4, up to 4 expansion cohorts will be included to further evaluate the safety, tolerability, efficacy, PK, and PD of RP2Ds selected from Part 3.

3.2.4.1. Sample Size in C-TGA and C-TGB

A Simon 2-stage design (Simon 1989; see Table 1) will be used for combination expansion cohorts C-TGA E1, C-TGB E1, and the optional C-TGA E2. The response rates for the historical control (p_0), desired response rates for the combination (p_1), number of subjects needed in Stage 1 (n_1) and Stage 2 (n_2), total number of subjects in both stages (n), first stage threshold to declare cohort undesirable (r_1), upper limit of the number of responses in n patients such that futility of the drug is concluded (r), and PET under p_0 (PET[p_0]) are provided for each of these expansion cohorts. The calculation is based on a 1-sided Type I error of 0.05 and power of 80%.

Table 1: Simon 2-Stage Design

Cohort	p_0	p_1	n_1	n_2	n	r_1	r	PET[p_0]
C-TGA E1	20%	40%	13	30	43	3	12	0.7473
C-TGB E1	20%	40%	13	30	43	3	12	0.7473
C-TGA E2 (optional)	20%	40%	13	30	43	3	12	0.7473

3.2.4.2. Sample Size in C-TGC

Up to 16 subjects will be enrolled in the C-TGC E1 cohort. The sign test will be used to evaluate change and percentage change from baseline in spleen volume by MRI or CT in applicable subjects with a 1-sided Type I error of 0.05. Assuming the percentage reduction is normally distributed with a mean of 15 and standard deviation of 14.5, the test has 92.2% power to indicate whether additional development is warranted.

3.3. Schedule of Assessments

See Protocol Amendment 6 dated 15 MAR 2017 for a full description of all study procedures and assessment schedules for this study.

4. DATA HANDLING DEFINITIONS AND CONVENTIONS

4.1. Scheduled Study Evaluations and Study Periods

4.1.1. Day 1

For monotherapy, Day 1 is the date that the first dose of INCB053914 is administered to the subjects.

For combination therapy, Day 1 is the date that the first dose of any of the study drugs (INCB053914, cytarabine, azacitidine, or ruxolitinib) is administered to the subjects.

4.1.2. Study Day

If a visit/reporting date is on or after Day 1, then the study day at the visit/reporting date will be calculated as

$$\text{Day \#} = (\text{Visit/Reporting Date} - \text{Day 1 date} + 1).$$

If the visit/reporting date is before Day 1, then the study day at the visit/reporting date will be calculated as

$$\text{Day \#} = (\text{Visit/Reporting Date} - \text{Day 1 date}).$$

A study day of -1 indicates 1 day before Day 1.

4.1.3. Baseline Value

For monotherapy, baseline is the last nonmissing measurement obtained before the first administration of INCB053914.

For combination therapy, baseline is the last nonmissing measurement obtained before the first administration of INCB053914, cytarabine, azacitidine, or ruxolitinib.

When scheduled assessments and unscheduled assessments occur on the same day, and the time of the assessment or time of first dose is not available, use the following convention to determine baseline:

- If both a scheduled and an unscheduled visit are available on the day of the first dose and the time is missing, use the scheduled assessment as baseline.
- If all scheduled assessments are missing on the day of the first dose and an unscheduled assessment is available, use the unscheduled assessment as baseline.

4.1.4. Handling of Missing and Incomplete Data

In general, values for missing data will not be imputed unless methods for handling missing data are specified in this section or relevant sections.

Missing or partial disease/cancer diagnosis date will be handled as follows:

- If only the day is missing, then the imputed day will be the first of the month.
- If both the month and day are missing, then the imputed day and month will be 01 JAN.
- No imputation will be done if the date is completely missing.

Missing or partial date of last dose will be handled as follows:

- If only the day is missing, then the imputed date of the last dose will be the earlier date of the first day of the month or the date that the subject discontinued treatment.
- Otherwise, the date that the subject discontinued treatment will be used as the date of the last dose.

For relevant efficacy endpoints, partial death date will be imputed as follows:

- If mmyyyy for the last contact date = mmyyyy for the death date, then the death date will be set to the day after the last contact date.
- If mmyyyy for the last contact date < mmyyyy for the death date, then the death date will be set to the first day of the death month.
- Otherwise, the partial death date will not be imputed.

For prior and concomitant medications:

The start/stop dates recorded in the eCRF by the investigator and his or her research staff will be used to identify when a concomitant medication was taken during the study. Any missing start date must be queried for resolution. Unresolved missing start dates will be handled as follows:

- If the date is completely missing, the medication will be considered both prior and concomitant.
- If only the day is missing, and the last day of the month is before the first dose date on Day 1, then the concomitant medication will be considered as starting before Day 1, and the incomplete date will be imputed as the last day of the month.
- If only the day is missing, and the first day of the month is after the first dose date on Day 1, then the concomitant medication will be considered as starting after Day 1, and the incomplete date will be imputed as the first day of the month.
- If only the day is missing, and the month is equal to the month of the first dose date on Day 1, then the incomplete date will be imputed as the first day of the month.
- If both the month and day are missing, and the last day of the year is before the first dose date on Day 1, then the concomitant medication will be considered as starting before Day 1, and the incomplete date will be imputed as the last day of the year. Otherwise, the incomplete date will be imputed as the first day of the year.

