5.2. Treatment Groups

This is an open-label, dose-escalation study of the PIM kinase inhibitor INCB053914 as monotherapy and in combination with standard-of-care agents in subjects with advanced malignancies. The study will be conducted in 4 parts: Parts 1 and 2 will evaluate INCB053914 as monotherapy and Parts 3 and 4 will evaluate INCB053914 in combination with select standard-of-care agents.

In Part 1, subjects will be enrolled in 1 of 2 treatment groups. The initial dose level in each treatment group will be 100 mg QD, with dose increases up to 2-fold until a Grade 2 toxicity that has a reasonable possibility of being related to INCB053914 is observed in that treatment group or until a total daily dose of 300 mg has been reached in that treatment group, after which dose increases will be limited to $\leq 50\%$. Alternate administration, such as intermediate doses, alternate dose regimens, or alternate formulations, may also be implemented depending on emerging PK, PD, and safety results.

In Part 2, subjects will be enrolled in up to 5 expansion cohorts (TGA A1, TGA A2, TGA A3, TGB B1, and TGB B2), as defined in [Section 3](#), at the RP2Ds identified in Part 1.

Part 3 will comprise up to 3 disease-specific treatment groups: C-TGA, C-TGB, and C-TGC, as defined in [Section 3](#). The starting dose of INCB053914 in the combination treatment groups will be a PAD and a dose level below the highest tolerated dose of INCB053914 monotherapy identified in Part 1 of this study. As of the most recent data cutoff date (at the time of Amendment 6), the highest tolerated dose of INCB053914 monotherapy was 80 mg BID, which also met the Protocol-defined criteria for a PAD; thus the starting dose for Part 3 will be 65 mg BID (Dose Level 1 dose). The INCB053914 dose used in Part 3 will never exceed the monotherapy MTD dose to be identified in Part 1 of the study.

[Table 2](#), [Table 3](#), and [Table 4](#) summarize the dose regimens to be used in the standard-of-care combination dose-finding cohorts. An alternative starting dose and/or subsequent INCB053914 doses may be selected pending emerging Part 1 safety, PK, and PD data.

Table 2: Planned C-TGA Combination Dose-Finding Cohorts

Dose Level	I-DAC Dose	INCB053914 Dose ^a	Treatment Group
-1	1 g/m ² ; given as 2-hour infusion on Days 1-5 ^b	50 mg BID	C-TGA 50 mg BID
1 (starting dose)	1 g/m ² ; given as 2-hour infusion on Days 1-5	65 mg BID	C-TGA 65 mg BID

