6.4.1. Exposure for INCB053914

- **Duration of treatment (days):** Date of last dose of INCB053914 – date of first dose of INCB053914 + 1.
- **Total dose administered (mg):** Sum of INCB053914 doses administered (mg) across cycles.
- **Average Daily Dose (mg/day):** Total dose administered (mg) / duration of treatment (days).

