6.4.4. Exposure for Ruxolitinib

- **Duration of treatment (days):** Date of last dose of ruxolitinib – date of first dose of ruxolitinib + 1.
- **Total dose administered (mg):** Sum of ruxolitinib administered (mg) across cycles.
- **Average Daily Dose (mg/day):** Total dose administered (mg) divided by the duration of treatment in days.

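### A last-dose date missing only its day is imputed to the first of the month, with no floor at first dose: exposure is almost always shortened, and duration can be zero or negative.

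*SAP*

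**What the plan says.** SAP 4.1.4 has two rules for an incomplete last-dose date.

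- Only the day missing: "the imputed date of the last dose will be the earlier date of the first day of the month" or the treatment-discontinuation date.
- Any other gap: "Otherwise, the date that the subject discontinued treatment will be used as the date of the last dose".

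Neither rule compares the result with the first-dose date.

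SAP 6.4.1 defines INCB053914 treatment duration as "Date of last dose of INCB053914 – date of first dose of INCB053914 + 1", and average daily dose as total dose divided by that duration. Total dose is "Sum of INCB053914 doses administered (mg) across cycles", so it does not depend on the imputed date. SAP 6.4.4 repeats the construction for ruxolitinib: "Date of last dose of ruxolitinib – date of first dose of ruxolitinib + 1".

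Exposure to cytarabine and azacitidine (SAP 6.4.2 and 6.4.3) is built from administrations and doses and uses no last-dose date.

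**The concern.** The first of the month is the earliest date that fits a known month, and taking the earlier of two dates can only move it further back. The discontinuation date therefore acts only if it precedes the recorded month of last dose, which would be a data inconsistency. The error runs one way. Total dose stays fixed while its divisor shrinks, so average daily dose rises.

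The rule also sits oddly beside the one that follows it. A subject whose month is missing as well receives the discontinuation date, usually a closer estimate, so knowing the month makes the result worse. The concomitant-medication rules in the same section do compare an incomplete date with Day 1; the last-dose rule does not.

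What is at stake is the exposure table, planned for all four Parts and marked for in-text use (SAP Appendix A). Descriptive summaries include the minimum (SAP 5.1), so one negative duration would be printed as such. Parts 1 and 3 are summarised by dose level (SAP 5.2), with 3 to 6 subjects per cohort (SAP 3.2.1 and 3.2.3), so one affected subject can be visible.

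**Working it through.** The documents give no figure to reproduce, so I applied the rules directly.

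**Inputs.** Imputed last dose = min(first of month, discontinuation date), from SAP 4.1.4. Duration = last - first + 1, and average daily dose = total dose / duration, from SAP 6.4.1 and 6.4.4. Expected treatment of about 4 to 6 months (Protocol 4.4) is taken as 120 to 180 days. For illustration only, the daily dose is 2 x 65 = 130 mg, from SAP 5.2: "thus the starting dose for Part 3 will be 65 mg BID". Discontinuation is assumed to fall on or after the last dose.

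**Days lost.** If the true last dose was on day *d* of its month, the loss is *d* - 1, from 0 to 30. With every date of a 365-day year equally likely:

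- mean loss = (7 x 465 + 4 x 435 + 378) / 365 = 5373 / 365 = 14.7 days, where 465, 435 and 378 are the sums of *d* - 1 over months of 31, 30 and 28 days;
- no loss on 12 / 365 = 3.3% of dates (the 1st of each month).

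**Relative size.**

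- Duration: 14.7 / 180 = 8% to 14.7 / 120 = 12% too short.
- Average daily dose: 180 / 165.3 = 1.09 to 120 / 105.3 = 1.14, so 9 to 14% too high.
- Mean duration in a cohort with one affected subject: down by 14.7 / 6 = 2.5 to 14.7 / 3 = 4.9 days.

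**First and last dose in the same month.** The imputed date is the 1st, so duration = 1 - (day of first dose) + 1 = 2 - (day of first dose).

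| First dose on | Duration (days) | Average daily dose |
|---|---|---|
| 1st | 1 | whole total dose assigned to one day |
| 2nd | 0 | undefined |
| 10th | -8 | negative |
| 31st | -29 | negative |

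**How short treatment must be.** A negative value needs a first dose on the 3rd or later and a last dose in the same month. For true duration *T* in a month of *L* days, that is *L* - *T* - 1 start dates (none if this is below zero). Over the year, given that the day is missing:

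| True duration (days) | Start dates giving a negative duration |
|---|---|
| 7 | 269 / 365 = 73.7% |
| 14 | 185 / 365 = 50.7% |
| 21 | 101 / 365 = 27.7% |
| 28 | 18 / 365 = 4.9% |
| 42 or more | 0% |

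**Worked cases at 130 mg/day.**

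- First dose 15 March, last dose 28 March: truly 14 days and 1820 mg. The rule gives -13 days and 1820 / -13 = -140 mg/day.
- First dose 15 January, last dose 20 May, discontinuation 22 May: truly 126 days and 16,380 mg. With the day missing, the rule gives 107 days and 16,380 / 107 = 153.1 mg/day. With the month missing too, the discontinuation date gives 128 days and 16,380 / 128 = 128.0 mg/day.

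**The case against.** The strongest reply is that little depends on this. Exposure is only summarised descriptively. Compliance (SAP 6.5) does not use duration. DLT evaluability rests on 80% of planned doses (Protocol 5.2.3), and treatment-emergent events are counted from the first dose (SAP 10.2.1). The readable ORR and Simon rules make no use of the last-dose date. The rule may also seldom apply: Protocol 5.2.7.2 requires the last-dose date in the eCRF, reminder cards record the last dose before each visit (Protocol 7.10.2), and tablets are counted (Protocol 5.1.7). All of this stands, and it keeps the point small.

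It can also be said that first-of-month is a cautious convention and month-end only a different one. That holds in part. The missing floor at first dose is an error whichever convention is preferred. Replacing first-of-month is a judgement, though it agrees with the SAP's own rule for less complete dates.

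A reader might infer more than the text supports:

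- That every partial last-dose date is affected. Only dates missing the day alone are; the rest take the discontinuation date.
- That exposure is always shortened. A true last dose on the 1st loses nothing.
- That every same-month case gives zero or less. A first dose on the 1st gives 1 day.
- That negative values are likely in AML. The documents give no distribution of treatment duration in AML. Protocol 1.4.2 reports 28 of 34 subjects off treatment without saying when, Protocol 4.4 expects 4 to 6 months on average, and inclusion criterion 6 asks for a life expectancy above 12 weeks.

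**Conclusion.** The point holds for last-dose dates that lack only the day. For those, the stated rule is biased in one direction and, when treatment starts and ends in the same calendar month, can return an impossible duration. This is a defect in a written rule, not an omitted detail.

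It is a minor one. It reaches only the duration and average-daily-dose summaries for INCB053914 and ruxolitinib, and only for affected subjects, whose number the documents do not allow one to estimate. No primary-endpoint, DLT or dose-escalation rule in the readable text changes. The 14.7-day mean assumes that last doses are spread evenly over the calendar, and the percentages assume 120 to 180 days of treatment. The same-month formula needs only that discontinuation is not dated before the first of that month.

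**What to change.** Replace the day-only rule in SAP 4.1.4 with one sentence: when only the day is missing, impute the earlier of the last day of that month and the treatment-discontinuation date, but never a date before the first dose or the last date with documented dosing.

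In the two worked cases this gives 14 days and 130 mg/day (discontinuation also on 28 March), and 128 days and 128.0 mg/day. The floor rules out zero and negative durations. The discontinuation date then works as a real upper limit, consistent with the rule for less complete dates.

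The cost is one SAP sentence and the matching derivation; no new data are needed. The drawback is that duration may be slightly overstated when discontinuation is recorded after the true last dose: 2 days in the second case, against 19 days understated (126 - 107) under the present rule.
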